## 9.2.2 Secondary Outcome Measures

- The frequency and severity of symptomatic, medically attended respiratory and febrile illness in the RSV-seronegative (group 2) vaccine and placebo recipients who experience natural infection with wt RSV during the first RSV season and through the second RSV season for group 2 subjects who participate in a second RSV season surveillance.
- The antibody responses in the RSV-seronegative vaccine and placebo recipients who experience natural infection with wt RSV during the first RSV season and during a second RSV season for those who choose to participate.
- The quality and epitope specificity of RSF F-specific antibody

## 9.3 SAMPLE SIZE AND ACCRUAL

### 9.3.1 Sample Size and Randomization

In group 1, approximately 15 RSV-seropositive children will be enrolled in the study and will receive either  $10^{5.7}$  PFU of vaccine or placebo, at a ratio of 2:1. In group 2, approximately 21-30 RSV-seronegative infants and children will be enrolled in the study and will receive either  $10^{5.0}$  PFU of vaccine or placebo at a ratio of 2:1. If 30 seronegative participants are enrolled, we anticipate that 20 seronegative vaccinees and 10 seronegative placebo recipients will provide data for the primary objectives. The sample size was chosen based upon past experience with phase I evaluation of other live-attenuated respiratory virus candidate vaccines (24-26). The 2:1 randomization ratio will be used to maximize the information obtained regarding the response of children to the RSV 6120/ANS2/1030s vaccine. In the event that a participant is discontinued early from the study and the team decides that additional data would be needed to answer the study objectives, an additional participant may be enrolled in the same treatment arm as the discontinued participant.

Eligible subjects whose parents/guardians decline participation in the second RSV season surveillance will not be replaced.

Given the small sample size, the study will have limitations with respect to detecting AEs and estimating the rates of such events in the population represented by the study sample.

The following calculations focus on the assessment of the tolerability of the vaccine and, in particular, occurrence of LRI, which occurs very infrequently in children who participate in these types of studies but would be considered a sentinel safety event if observed in children infected with vaccine virus.

Table 24 shows the probability of observing 0 events of LRI within the sample of 20 seronegative vaccinees, as well as the probability of observing 1 or more events or 2 or more events, under a range of assumptions concerning the true rate of such events in the participant population represented by this sample. From this table, it can be seen that if the true proportion of LRI (or other AE) is at least 10%, there is a 61% chance of observing 2 or more events in a group of size 20, and an 88% chance of observing at least a single event.

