## **3 STUDY DESIGN**

The study will be double-blind, randomized, and placebo-controlled. Participants in groups 1 and 2 will be block-randomized in groups of 3 at a ratio of 2:1 to receive vaccine or placebo, respectively. The vaccine will be evaluated in a stepwise fashion beginning with RSV-seropositive children (Group 1) and proceeding sequentially in RSV-seronegative children (Group 2). For the purpose of this study, RSV-seropositive is defined as having a serum neutralizing antibody titer of  $\geq 1:40$ , and RSV-seronegative is defined as having a serum neutralizing antibody titer of  $< 1:40$ . This definition has been used in previous evaluations of live-attenuated RSV vaccines (11, 24, 35). In these previous studies, live-attenuated RSV vaccines were highly restricted in replication and poorly immunogenic in children with titers  $\geq 1:40$  but were far less restricted in replication and highly immunogenic in children with titers  $< 1:40$ . These data suggest that this neutralizing antibody cutoff can distinguish effectively between RSV-experienced and RSV-naïve children.

The study will proceed to group 2 if there are not more than 2 vaccine-associated solicited AEs and no vaccine-associated LRIs in RSV-seropositive children. If 3 or more RSV-seropositive children have respiratory or febrile illness that coincides with shedding of  $> 10^{2.5}$  PFU of vaccine virus as detected by culture, then we will enroll an additional 15 RSV-seropositive children to continue evaluating the safety, infectivity, and immunogenicity of the vaccine virus.

Enrollment occurs at the time of inoculation with study product, Day 0, and will occur between April 1 and October 31 to avoid the time during which wt RSV typically circulates in the community ([Appendix V](#), Figure 6). Accrual will stop prior to November 1.

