## **4.11 PARTICIPANT WITHDRAWAL OR TERMINATION FROM THE STUDY**

Participants in this study may voluntarily withdraw from the study at any time. Any participant who has received study product will be encouraged to remain in the safety evaluation for the duration of the study even if sample collection is refused.

A participant may withdraw or terminate participation in the study early for any of the following reasons:

- Withdrawal of consent – applies to a parent/guardian who verbally or in writing withdraws consent for the participant to continue in the study for any reason.
- Noncompliant with protocol – applies to a parent/guardian who does not comply with protocol-specific visits or evaluations on a consistent basis, such that adequate follow-up is not possible and the participant's safety would be compromised by continuing in the study.
- Investigator discretion – participant withdrawal may occur if the investigator believes that it is in the best interest of the participant.
- Other – a category used when previous categories do not apply; requires an explanation.

The study may be ended for the following reasons:

- Research is terminated by sponsor or investigator – applies to the situation where the entire study is terminated by the sponsor or investigator for any reason.
- The study sponsor, CIR, the institutional review board (IRB), the Office for Human Research Protections (OHRP), NIAID, or the US Food and Drug Administration (FDA) may decide to end the study.

For any participant who withdraws or who is terminated from the study prior to completion of follow-up, study staff will document the reason for the withdrawal or termination. In the event that the circumstances that led to a participant's withdrawal or termination change, the study staff will contact the PI to discuss options for resumption of follow-up. Withdrawn subjects will not be replaced.

Participants enrolled in the optional second year of RSV season surveillance may voluntarily withdraw before the conclusion of the second year RSV surveillance season.

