### **6.3 RANDOMIZATION**

Randomization numbers will be assigned by the unblinded laboratory vaccine dispenser and will be forwarded to the Data Safety Monitoring Board (DSMB) Executive Secretary. Unblinded laboratory personnel will label the vaccine syringes with the study virus vaccine name, PI initials, study number, subject's randomization number, preparer and vaccine verifier's initials and expiration date and time. The vaccine administrator and verifier will initial the label and place the label in the subject's study chart. The vaccination time will be documented on the vaccine administration record (VAR). All syringes will be disposed of by the study staff following the enrollment visit. A copy of the VAR will be sent to the laboratory.

A copy of the randomization code will be retained by the unblinded dispenser in the laboratory where the vaccine is prepared. Without the PI's written request to unblind, the randomization code will not be released to the clinical staff until the acute monitoring phase is complete for each subject within the randomization group. Pediatric subjects will be block-randomized in groups of 3 (2 vaccinees and 1 placebo recipient per block); this allows for maintenance of the blind during each subject's acute monitoring phase but also provides early information regarding safety, which is appropriate and common practice for phase 1 respiratory virus vaccine studies (11,23,25). Detailed procedures for randomization and unblinding will be placed in the laboratory study binder.

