## **9.5 ANALYSES**

### **9.5.1 Assessment of Primary Objectives**

Safety data from all participants in CIR 322 who have been inoculated will be summarized together, including data from participants who discontinue study early or have some missed visits. In the immunogenicity analyses, those who do not provide data for the Day 28 Visit follow-up for RSV-seropositive participants and for the Day 56 Visit follow-up for RSV-seronegative participants (due to early discontinuation or missed visit) will be treated as “failures.” Sensitivity analyses will be performed to check if the results are consistent with those when these participants are excluded. Participants who receive any of the disallowed treatments listed in Section 5.10 during the first 28 days after inoculation for RSV-seropositive participants and during the first 56 days after inoculation for RSV-seronegative participants may be excluded from the immunogenicity evaluations after the time of the treatment. These participants, however, will be included in the safety evaluations for the duration of the study. These participants will not be replaced. Details of the analyses listed below will be included in the statistical analysis plan.

The frequency of solicited AEs and unsolicited AEs, along with 90% confidence intervals, during Study Days 0 to 10 in RSV-seropositive subjects and during Study Days 0 to 28 in RSV-seronegative subjects and of vaccine-related SAE during Study Days 0 to 28 in RSV-seropositive subjects and during Study Days 0 to 56 in RSV-seronegative subjects will be summarized. In addition, line listing of individual clinical solicited AEs and unsolicited AEs, graded by severity, will be prepared for events occurring during Study Days 0 to 10 in RSV-seropositive subjects and during Study Days 0 to 28 in RSV-seronegative subjects and vaccine-related SAE during Study Days 0 to 28 in RSV-seropositive subjects and during Study Days 0 to 56 in RSV-seronegative subjects.

The proportion of participants with infection defined as recovery of vaccine virus from a nasal wash as determined by culture and RT-PCR, and/or a  $\geq 4$ -fold rise in neutralizing antibody titer to RSV, will be summarized. A line listing of the individual peak titer of vaccine virus shed and duration of virus shedding in nasal washes by each individual will be prepared. In addition, the geometric mean peak titer and mean duration of virus shed will be provided for each treatment group.

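### Section 9.3.1 lets a discontinued child be replaced in the same treatment arm, which contradicts Section 4.11, is not random allocation, and leaves the blind and the denominator undefined.

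*Combined protocol and SAP*

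**What the plan says.** Section 9.3.1 provides that, after an early discontinuation, "an additional participant may be enrolled in the same treatment arm as the discontinued participant". The stated condition is that "the team decides that additional data would be needed to answer the study objectives". The section does not define the team or say whether its members are blinded.

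Section 4.11, on withdrawal and termination, states "Withdrawn subjects will not be replaced" and gives no exception. Two other sentences are narrower. In Section 9.5.1, "These participants will not be replaced" refers to recipients of disallowed treatments. In Section 9.3.1, "Eligible subjects whose parents/guardians decline participation in the second RSV season surveillance will not be replaced" concerns the optional second season only. Neither conflicts with the replacement provision.

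On allocation, Section 3 states "The study will be double-blind, randomized, and placebo-controlled", and Section 6.3 states "Pediatric subjects will be block-randomized in groups of 3 (2 vaccinees and 1 placebo recipient per block"). The unblinded dispenser keeps the code. Unless the principal investigator asks in writing for unblinding, "the randomization code will not be released to the clinical staff until the acute monitoring phase is complete for each subject within the randomization group". The acute phase ends on Day 10 in group 1 and Day 28 in group 2.

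Section 9.5.1 keeps every inoculated child in the safety summary. In the immunogenicity analyses it counts a child without Day 28 (group 1) or Day 56 (group 2) data as a failure, with a sensitivity analysis excluding such children.

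**The concern.** Staff facing a dropout can point to either rule, and nothing in the protocol distinguishes a withdrawn child from a discontinued one. Under 9.3.1 the new child enters by a discretionary decision and without randomization.

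Block codes are released progressively, so the people deciding may already know the lost child's arm. In that case the replacement's arm is known before inoculation. This matters for safety because the study clinician judges each adverse event as related or not related (Section 8.1), and the primary safety outcomes are product-related events (Section 9.2.1).

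The third difficulty is the count. In a group of 14 to 20 vaccinees one child is worth 5 to 7 percentage points (1/20 = 5%, 1/14 = 7.1%). Section 2.1 calls the vaccine over-attenuated if fewer than 70% of seronegative vaccinees are infected. Near that value, the treatment of the lost child and the replacement can matter.

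**Working it through.** **1. The two rules.** Section 4.11 covers participants who withdraw or are terminated before completing follow-up and bars replacement. Section 9.3.1 covers participants discontinued early and permits it. These are the same children, and no text gives one section precedence.

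**2. Allocation probability.** A child entering through a block of three (2 vaccine, 1 placebo) has a prior probability of vaccine of 2/3. A same-arm replacement has probability 1 if the lost child was a vaccinee and 0 if a placebo recipient. Sections 3 and 6.3 describe no mechanism for a replacement.

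**3. When the arm can be known (group 2).**
- Lost before the block's code is released: the dispenser can match the arm silently. The two allocations are nevertheless linked, so if the block is released during the replacement's own acute phase, anyone who knows the link learns the new child's arm.
- Lost between Day 28 and Day 56: the block may already be released, so the arm may be known when the replacement is inoculated. These losses remove the Day 56 serum, and hence the primary antibody endpoint, so they are a likely reason to want a replacement.

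**4. The denominator at the 70% threshold.** Assume that the lost vaccinee was not infected and the replacement was.

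| Vaccinees | No replacement | Both counted | Lost child removed |
|---|---|---|---|
| 20 | 13/20 = 65.0% | 14/21 = 66.7% | 14/20 = 70.0% |
| 14 | 9/14 = 64.3% | 10/15 = 66.7% | 10/14 = 71.4% |

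Only the last column reaches 70%. The plan does not state which column applies.

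**5. The cost of not replacing.** The plan's own figure comes first: 80% power with 20 vaccinees and 10 placebo recipients, one-sided Fisher's exact test, alpha 0.05 (Section 9.3.1, Table 26). Power is the sum of Bin(x; n_V, p_V) × Bin(y; n_P, p_P) over all outcomes (x, y) whose hypergeometric upper-tail p-value is at most 0.05.

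| Placebo / vaccine | 20 v 10 | 19 v 10 | 20 v 9 | Lost vaccinee counted as failure |
|---|---|---|---|---|
| 0.05 / 0.52 | 0.806 | 0.760 | 0.761 | 0.760 |
| 0.10 / 0.59 | 0.797 | 0.745 | 0.736 | 0.745 |
| 0.15 / 0.65 | 0.795 | 0.742 | 0.738 | 0.738 |
| 0.20 / 0.71 | 0.801 | 0.756 | 0.755 | 0.741 |
| 0.50 / 0.95 | 0.797 | 0.805 | 0.736 | 0.637 |

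The first column reproduces the stated 80%. The next two exclude the lost child. The largest fall is 0.797 − 0.736 = 0.061. One entry rises slightly because the exact test is discrete. The last column applies the failure rule of 9.5.1: x is drawn from Bin(19, p_V) and tested as x out of 20. It is similar in the first four rows but falls to 0.637 at 0.50 / 0.95.

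For zero events among n vaccinees, the exact 90% upper limit is 1 − 0.05^(1/n). It is 13.9% at n = 20, matching the 14% in Table 25, and 14.6% at n = 19.

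**The case against.** The best defence is that replacement can be legitimate in a small phase I study and that this plan has no dropout allowance: it expects 20 + 10 evaluable children from 30 enrolled. The provision is optional, and Section 9.1.2 describes the study as exploratory. Detailed randomization and unblinding procedures are placed in a laboratory binder that is not part of these documents. All of that stands, but a binder cannot reconcile two opposing protocol rules.

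Three stronger readings are tempting, and the documents do not support them.

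- *Replacement necessarily unblinds both children.* It does not. The dispenser holds the code, prepares masked syringes and is responsible for the blind (Sections 5.5, 5.7, 6.3), so the arm could be matched without telling clinical staff. Release of the lost child's block after the acute phase is planned in any case. The risk depends on timing.
- *Section 9.5.1 makes replacement impossible, because a child cannot be both counted as a failure and substituted.* Section 9.3.1 speaks of an additional participant and does not say that the discontinued child is removed, so both can be counted. The failure rule is also confined to immunogenicity. The gap is that the denominator is not stated.
- *One replacement decides the over-attenuation verdict.* With both children kept, 14/21 is still below 70%. The verdict changes only if the lost child is removed, which no section provides for. The example also fails if that child had already shed vaccine virus, since a positive nasal wash alone counts as infection (Section 9.2.1).

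**Conclusion.** The concern holds in a limited form. Sections 4.11 and 9.3.1 contradict each other. Same-arm placement is not random allocation under the 2:1 blocks of three, and the decision rests with an undefined team that is not required to be blinded. These points follow from the text and need no assumption.

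Disclosure of the replacement's arm is possible but not automatic. It is most plausible for a group 2 child lost between Day 28 and Day 56, and it assumes that staff know which child is being replaced.

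The effect on the 70% criterion is an ambiguity of 14/20 against 14/21 (70.0% against 66.7%). It rests on three assumptions: the lost vaccinee was not infected, the replacement was infected, and the result lies at the threshold. It is an illustration and not a forecast. The criterion concerns vaccinees only, so the example shows the open denominator; it does not measure bias in the randomized comparison.

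**What to change.** Delete the replacement sentence in Section 9.3.1 and keep Section 4.11 as the single rule. If more data are wanted, enrol a further complete randomized block of three within the planned 21 to 30, and keep every inoculated child in the analysis as Section 9.5.1 states. State that the discontinued child stays in the denominator and, because the failure rule covers only immunogenicity, how that child is classified for infection.

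The cost is some precision. With the lost child excluded, power for the Table 26 differences is about 74-81% after one loss, against about 80%. If a lost vaccinee is counted as a failure it is 0.74-0.76 in the first four rows and 0.637 in the last. Losing one vaccinee raises the zero-event upper limit from 13.9% to 14.6%. A further block enrols three children to make up for one, and once 30 are enrolled there is no room for it without changing the planned size.

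If the sponsor prefers to keep replacement, Section 4.11 must be amended to match. The protocol should then name a blinded decision-maker, state how the new child is assigned and when that code is released, and say how both children are analysed.

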**Table 24: The Probability of Observing LRI Events in Seronegative Vaccine Recipients**

		N = 20		
True underlying probability of LRI or AEs	Pr (0 events)	Pr (1+ events)	Pr (2+ events)	
.01	0.82	0.18		0.02
.03	0.54	0.46		0.12
.05	0.36	0.64		0.26
.1	0.12	0.88		0.61
.15	0.04	0.96		0.82

Table 25 presents 90% confidence intervals (CIs) around potential rates of LRI or AEs that might be observed in the sample of 20 vaccine recipients. The CIs around similar rates in a sample of 10 placebo recipients are also presented. Note that if no LRI or AEs are detected among the 20 vaccine recipients, we are 90% confident that the true probability of AEs in the population from which the sample is drawn is between 0 and 14%.

**Table 25: Percent of Participants Experiencing LRI or AEs with Exact 90% CI**

[figure not shown]
N	% LRI or AEs	90% CI
10	0%	0% -- 26%
20	0%	0% -- 14%
10	10%	1% -- 39%
20	10%	2% -- 28%
10	20%	4% -- 51%
20	20%	7% -- 40%
10	30%	9% -- 61%
20	30%	14% -- 51%

Group sample sizes of 20 in the vaccinated group and 10 in the placebo group would achieve 80% power to detect a difference between the group proportions of about 0.45. The test statistic used is the one-sided Fisher's exact test. The alpha level of the test was targeted at 0.05. Table 26 presents examples of true group differences which can be detected with 80% power, and Figure 5 graphically shows power curves for 90% power, 80% power, and 70% power given the sample sizes.

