**Table 26: Magnitude of Difference in Responses Detectable with 80% Power**

Response Proportion in the Placebo Group	Response Proportion in the Vaccinated Group	Difference
0.05	0.52	0.47
0.1	0.59	0.49
0.15	0.65	0.50
0.2	0.71	0.51
0.5	0.95	0.45

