The proportion of participants that develop 4-fold or greater rises in RSV-neutralizing antibody titer following vaccination will be summarized. A line listing of the individual RSV antibody titer pre- and post-vaccination will be prepared. In addition, the geometric mean and median antibody titers will be provided for each treatment group. Line listings of individual RSV-neutralizing antibody responses as well as of antibody responses to the RSV F glycoprotein will be prepared as well.

Where appropriate, a 1-tailed Wilcoxon rank sum test will be used to test the hypothesis that the vaccinated group will exhibit greater peak viral titers and antibody titers following vaccination compared to the placebo group. A 1-tailed Fisher’s exact test will be used to test the hypothesis

that the vaccinated group will exhibit a greater proportion of participants who develop fourfold or greater rises in RSV-neutralizing antibody titer following vaccination compared to the placebo group.

These will be the only formal statistical comparisons between the vaccinated and placebo groups. These tests will be carried out at a 5% significance level.

The study results will be compared with the criteria listed in Section 1.1 to determine if this vaccine is a promising candidate for further evaluation in expanded phase I studies or phase II studies.

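### The 80% power quoted for a difference of about 0.45 at 20 vs 10 holds only for placebo response near 0 or near 50%, and the permitted 14 vs 7 size has no stated power or precision

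*Combined protocol and SAP*

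**What the plan says.** The power statement is in Section 9.3.1, between Tables 25 and 26. It takes 20 vaccinees and 10 placebo recipients and claims that these numbers "would achieve 80% power to detect a difference between the group proportions of about 0.45". On method it adds: "The test statistic used is the one-sided Fisher's exact test", with a target alpha of 0.05. It names no placebo response. Table 26, titled "Magnitude of Difference in Responses Detectable with 80% Power", then lists five pairs of response proportions, with differences of 0.47, 0.49, 0.50, 0.51 and 0.45 at placebo responses of 0.05, 0.10, 0.15, 0.20 and 0.50.

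On the size of group 2, Section 9.3.1 says that "approximately 21-30 RSV-seronegative infants and children will be enrolled in the study", randomised 2:1. Table 1 in the Protocol Summary shows 14 to 20 vaccinees and 7 to 10 placebo recipients. Section 9.3.1 ties the 20 and 10 to an enrolment of 30. Table 24 is headed N = 20, Table 25 has rows for 10 and 20 only, and the accompanying text speaks of what follows "if no LRI or AEs are detected among the 20 vaccine recipients".

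Section 9.5.1 plans the same test for the analysis: a one-tailed Fisher's "exact test will be used to test the hypothesis" of a higher proportion of fourfold neutralizing-antibody rises in the vaccine group, at 5%.

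**The concern.** The summary sentence gives one number for the detectable difference, and that number is the most favourable of the five in the table it introduces. A reader who takes only the sentence will believe that 0.45 is detectable with 80% power whatever the placebo response.

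The second part matters more. A trial that enrols 21 seronegative children complies fully with the protocol, yet every power and precision figure for group 2 is worked at 20 or 20 vs 10. A board or regulator reading Section 9.3.1 cannot see what the smallest permitted trial delivers, either for the antibody comparison or for LRI, which that section treats as the sentinel safety event.

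**Working it through.** **Inputs.** Arm sizes 20 vs 10 (power statement) and 14 vs 7 (lower end of Table 1). One-sided Fisher's exact test, alpha 0.05 (Sections 9.3.1 and 9.5.1). Response pairs from Table 26. The documents state no expected placebo response, so it is varied as an assumption.

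**Method.** With X vaccine and Y placebo responders, power = Σ Bin(x; n_V, p_V) × Bin(y; n_P, p_P), summed over all (x, y) with one-sided hypergeometric p ≤ 0.05.

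**Step 1: reproduce Table 26, then repeat its pairs at 14 vs 7.**

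| Placebo | Vaccine | Difference | Power, 20 vs 10 | Power, 14 vs 7 |
|---|---|---|---|---|
| 0.05 | 0.52 | 0.47 | 80.6% | 53.0% |
| 0.10 | 0.59 | 0.49 | 79.7% | 58.0% |
| 0.15 | 0.65 | 0.50 | 79.5% | 59.8% |
| 0.20 | 0.71 | 0.51 | 80.1% | 61.3% |
| 0.50 | 0.95 | 0.45 | 79.7% | 59.1% |

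The table is right for the stated test.

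**Step 2: hold the difference at 0.45.**

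| Placebo | 20 vs 10 | 14 vs 7 |
|---|---|---|
| 0 | 87.0% | 45.4% |
| 0.05 | 76.9% | 47.8% |
| 0.10 | 72.0% | 48.8% |
| 0.15 | 69.8% | 49.1% |
| 0.20 | 68.6% | 49.2% |
| 0.30 | 67.6% | 49.1% |
| 0.40 | 68.8% | 50.4% |
| 0.50 | 79.7% | 59.1% |

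The first row can be checked by hand. With a placebo response of 0, Y is always 0. At either size the test then rejects when X ≥ 7, so power is P[Bin(20, 0.45) ≥ 7] = 0.870 or P[Bin(14, 0.45) ≥ 7] = 0.454. At 20 vs 10, power reaches 78% or more only for placebo responses up to about 0.04 or from about 0.495.

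**Step 3: difference needed for 80% power.**

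| Placebo | 20 vs 10 | 14 vs 7 |
|---|---|---|
| 0.05 | 0.467 | 0.589 |
| 0.10 | 0.491 | 0.601 |
| 0.15 | 0.503 | 0.610 |
| 0.20 | 0.510 | 0.615 |
| 0.50 | 0.451 | not reachable |

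In the last cell, even a 100% vaccine response rejects only when Y ≤ 4, and P[Bin(7, 0.5) ≤ 4] = 99/128 = 77%.

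**Step 4: safety precision.** The exact 90% upper limit after 0 events is 1 − 0.05^(1/n).

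- n = 20: 13.9% (the plan's 14%). n = 14: 19.3%.
- n = 10: 25.9% (the plan's 26%). n = 7: 34.8%.

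For a true event rate of 10%, P(2 or more) = 1 − 0.9^n − n × 0.1 × 0.9^(n−1).

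- n = 20: 1 − 0.122 − 0.270 = 0.608 (the plan's 61%).
- n = 14: 1 − 0.229 − 0.356 = 0.415, or 42%.

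P(1 or more) is 88% at n = 20 (as in Table 24) and 77% at n = 14.

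**Step 5: how much the choice of test costs.** The largest true size of the one-sided Fisher test at nominal 5% is 2.6% at 20 vs 10 and 2.2% at 14 vs 7. Boschloo's one-sided exact test has maximum size 4.8% and 4.6%. On the Table 26 pairs its power is 87% to 90% at 20 vs 10 and 72% to 77% at 14 vs 7. Its 80%-power difference for placebo responses of 5% to 20% is about 0.42 to 0.465 and 0.49 to 0.55 respectively.

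**The case against.** Nothing in the plan is miscalculated. Table 26 reproduces, sits immediately below the sentence and shows the larger differences to anyone who reads on; "about" also allows some slack. This stands, and it limits the first part to a loose summary.

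The placebo response may be low. Participants are seronegative and enrolled outside the RSV season, and Figure 5 is titled for vaccine virus shedding, where a placebo rate near 0 is natural. At 0, a difference of 0.45 has 87% power at 20 vs 10. This is a fair assumption, but the documents state no rate and Section 3 allows late enrolment to overlap the season. It also does not help the smaller size, where power at 0 is 45%.

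Every figure carries its own n, so a reader who infers that the safety precision is misstated goes too far: the 14 vs 7 figures are missing, not wrong. Section 9.3.1 does warn that a small sample limits detection and estimation of adverse events, but it does not quantify that for 14 vs 7.

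The consequence is limited. Section 9.1.2 calls the study exploratory, and the over-attenuation criterion in Section 2.1 is the proportion of vaccinees infected (below 70%), not a Fisher p-value. With a 5% placebo response, Fisher power at 14 vs 7 is 89% for a 70% vaccine response and 97% for 80%. Against that, it is only 56% at the 53% neutralizing response that Section 1.2 reports for the predecessor vaccine at 10^5 PFU.

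A reader might also infer that Fisher's test is a mistake here. It is not: it is valid, prespecified and the same test as in the power calculation. Conservatism is a reason to consider an alternative, not an error.

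**Conclusion.** The concern holds in two parts.

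First, as a general statement, 80% power for about 0.45 at 20 vs 10 is true only for placebo responses near 0 or near 50%. Between 5% and 40% the power is 68% to 77%, and the plan's own table asks for 0.47 to 0.51 at 5% to 20%.

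Second, and more important, the permitted 14 vs 7 size has no stated operating characteristics, and they are materially weaker. Power for 0.45 is 45% to 50% (placebo 0% to 40%), and 80% power needs about 0.59 to 0.62 (placebo 5% to 20%). After no events the upper 90% limit is 19% among 14 and 35% among 7. The chance of seeing two or more events at a 10% rate is 42%.

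These figures assume the stated test, full data on all randomised children, and a placebo response that the documents leave open. They do not show an arithmetic error in Table 26 or in the other reproduced figures. They also do not show that the trial is too small for its descriptive aims.

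**What to change.** In Section 9.3.1, restate the detectable difference as 0.45 to 0.51 depending on the placebo response (Table 26) at 20 vs 10, and about 0.59 to 0.62 at 14 vs 7 for placebo responses of 5% to 20%. Add n = 14 and n = 7, as applicable, to Tables 24 to 26 and to the confidence-interval text. The cost is wording and a few recomputed cells. Enrolment, visits and the analysis do not change, but the added 14 vs 7 figures will look less favourable.

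A separate, optional improvement is to replace the one-tailed Fisher test in Section 9.5.1 with Boschloo's one-sided exact test at 5%, which keeps the size below 5% and is never less powerful. If it is adopted, the Fisher wording above no longer applies. The sentence should then give about 0.42 to 0.465 at 20 vs 10 and 0.49 to 0.55 at 14 vs 7 (placebo 5% to 20%). The price is recomputing Table 26 and Figure 5 and using a less familiar test. The choice should be made before unblinded antibody results are seen.
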